6.6.4. Context and rationale for exposure(s) of interest

The exposure and comparator were defined to emulate the agents compared for the trial, i.e., initiation of palbociclib plus letrozole versus letrozole alone in a 1L metastatic setting.

- **EDB1:** Exposure is derived using a manually curated line of therapy (LOT) table provided by the data partner that programmatically categorizes treatment regimens into a coherent line of treatment, based on a proprietary business rule with an exposure assessment window. That is, each patient is represented with one row per curated line of therapy with corresponding information on line number, regimens as well start and end dates. Based on this table, patients are identified who received palbociclib-plus-letrozole or letrozole-alone treatment regimen by their generic names (string match) in 1L, using the exposure assessment window; follow-up begins after the end of the exposure assessment window. The LOT implicitly only considers regimens that were given as part of a metastatic disease setting. Importantly, the LOT table applies a proprietary business rule to determine line of therapy, which includes an exposure assessment window relative to advanced cancer diagnosis. More details and annotated code to identify initiators can be found in the 'Derive cohort EDB1' Quarto report (access within MGB network only).
- **EDB3:** Exposure is derived using a manually curated line of therapy (LOT) table provided by the data partner that programmatically categorizes treatment regimens into a coherent line of therapy, based on a proprietary business rule with an exposure assessment window. That is, each patient is represented with one row per curated line of therapy AND drug name with corresponding information online number, regimens as well start and end dates. Based on this table, patients are identified who received only palbociclib and letrozole within the first line of therapy, and letrozole alone within the first line of therapy by their generic names (string match), using the exposure assessment window; follow-up begins after the end of the exposure assessment window. The LOT implicitly only considers regimens that were given as part of a metastatic disease setting. More details and annotated code to identify initiators can be found in the 'Derive cohort EDB3' Quarto report' (access within MGB network only).
- **EDB4:** For the EDB4 database, the following logic is applied.

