- **EDB4:** Time in [days, months and years] from index date to death due to any reason. The date of death is de-identified to month-level granularity and the day of death is therefore imputed to the 15th of a month. If there is no indication that a patient died during the study period, the patient is censored. The censoring date is defined as the last date of vital signs recorded as proof that the patient was alive at that time (de-identified to week-level granularity) or data cut-off date, whichever occurred earlier. The OS endpoint is operationalized using a parameterized R function *edb4_get_os()* and more details can be found in the attached pdf documentation.

Table 4. Relevant clinical activities considered to derive last activity date for censoring.

Table / clinical activity considered	Dates considered
Adverse events	Event date
Therapy (cellular, systemic, radiation, surgery)	Start and end dates or declined intervention date, surgery date, assessed resection dates
Palliative care referral	Referral date
Visits	Contact/visit date
Vitals	Assessed date
Labs	Lab date
Biomarkers	Specimen collection date
Patient observation period	Start and end dates

Demographics	Date of most recent contact with provider, date patient was diagnosed with a second primary malignancy
Performance assessments	Documented date, reported date
Secondary diagnoses	Diagnosis date
Progression, histology, lymphovascular invasion, metastatic sites, pancoast tumor, perineural invasion	Assessed date
Stage/TNM	Assessed date
Smoking	Assessed date

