6.6.7. Context and rationale for covariates

We identified a series of covariates that are strong prognostic factors for the outcome and auxiliary covariates which may be useful to impute missing data. Such covariates comprise demographics, covariates indicating disease-severity, cancer-specific covariates as well as pathological and genetic factors. In addition, selected labs and vitals are considered since they were shown to carry a high amount of prognostic information as described in Becker, Weberpals, et al.¹¹ For these variables, additional plausibility checks and transformations are carried out. In detail, labs and vitals are individually checked if they cross a certain biologically implausible threshold (e.g., a heart rate of 0) in which cases the values are set missing and imputed in a next step. These thresholds were compiled by experienced practicing physicians and medical oncologists and are listed in appendix **Table 8** and **Table 9**.

Note that not all covariates are available across all databases used for this trial emulation. In the analytical stage, the most comprehensive model will be fit for each database individually.

Table 5. Operational definitions of key covariates used for trial emulation.

Characteristic	Harmonized analysis variable name	R function to derive covariate (see pdf in appendix)	Details ¹	Variable encoding	Assessment window
Age at index date	dem_age_index	edbx_get_demographics()	Age measured at index date	Binary (<60, 65+); modelled continuously in ROPRO ¹⁰	[0;0]
Year of index date	c_year_index	De novo derived from dt_index	Calendar year in which patient initiated study treatment	Nominal (<2020, 2020+)	[0;0]
Family history	dem_family_history	edbx_get_demographics()	Family history of cancer. Not available in EDB1.	Logical (TRUE, FALSE)	[0;0] (no specific date is associated)
Race	dem_race	edbx_get_demographics()	Race categorized as in the original RCT	Binary (Asian vs non-Asian)	[0;0]
Ethnicity	dem_ethnicity	edbx_get_demographics()	Ethnicity	Hispanic, Non-Hispanic	[0;0]
Region	dem_region	edbx_get_demographics()	US region patient receives care in; if given on a state level, region is manually mapped (see Table 10)	Nominal (Northeast, South, West, Midwest)	[0;0]
Practice type	dem_practice	edbx_get_demographics()	Setting patient is receiving care at. Not available in EDB3 and EDB4.	Nominal (academic, community, academic & community)	[-inf;0]

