Exclusion	Record of systemic anticancer therapy other than exposure/comparator on index date	Relevant	Possible	Possible	Possible	Not an explicit RCT criterion, added for database study

NCTID [NCT01740427](#)
Acronym **PALOMA2**
Protocol https://www.dropbox.com/sc/fi/cdxbn1ornvf4gb873km7/protocol_ico.23.00137.pdf?rlkey=pe8s1evdi6x3z6vzivbqapzf8&dl=0
SAP [not provided](#)
PMID 38252901
Indication Breast cancer
Line of Therapy Metastatic
Exposure palbociclib plus letrozole; 125 mg, orally once daily on Day 1 to Day 21 of every 28-day cycle followed by 7 days off treatment; in combination with Letrozole, 2.5 mg, orally once daily (continuously).
Comparisons placebo plus letrozole; Placebo orally once daily on Day 1 to Day 21 of every 28-day cycle followed by 7 days off treatment;
Emulated outcome Overall survival (secondary objective in original trial)

Measurement eligibility criteria						Comment	encore.io function
Criteria	Criteria rule as defined in original protocol	Time point/period of emulated measurement [days]	Emulation [EDB1]	Emulation [EDB3]	Emulation [EDB4]		
Inclusion 1	Adult women, aged at least 18 years.	[0; 0]	Age at index date (year granularity level); sex = female	Age at index date (year granularity level); sex = female	Age at index date (year granularity level); sex = female		edbx_get_demographics
Inclusion 2	Adenocarcinoma of the breast with locoregionally recurrent or metastatic disease not amenable to resection or radiation therapy with curative intent and for whom chemotherapy is not clinically indicated	[-inf; 0]	Mention of "non-squamous" histology; line of therapy needs to be for "Advanced" setting (LoT table)	Mention of "adenocarcinoma" histology; "First-line" in LoT table	Mention of "adenocarcinoma" histology; any evidence of at least one distant metastasis at any time before the index date (inclusive). This captures both de novo metastatic patients and those who progressed/developed metastases before/on the index date. First therapy for advanced disease after date of first metastasis	It depends on the database if there is a date associated with the recording of the histology, but usually the histology is determined around the time of diagnosis/staging. EDB4 does not have a well-curated line of therapy variable	edbx_get_histology(); EDB1 and EDB3: Part of exposure definition EDB4: Derived from edbx_get_diagnosis_solid()

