Inclusion 3	Documentation of histologically or cytologically confirmed diagnosis of estrogen-receptor positive (ER+) breast cancer based on local laboratory results.	[-inf; 0]	Any ER+ or ER missing status to or on index date	Any ER+ or ER missing status to or on index date	Any ER+ or ER missing status to or on index date	If ER is missing and a patient received the exposures of interest, then ER is likely to be positive given the alignment with the indication for the exposures of interest	edbx_get_biomarker()
Inclusion 4	Previously untreated with any systemic anti-cancer therapy for their locoregionally recurrent or metastatic ER+ disease.	[MBC; -1]	No systemic anti-cancer therapy following initial record potentially indicating metastatic disease and prior to index date	No systemic anti-cancer therapy following initial record potentially indicating metastatic disease and prior to index date	No systemic anti-cancer therapy following initial record potentially indicating metastatic disease and prior to index date		
Inclusion 5	Postmenopausal women defined as women with: - Prior bilateral surgical oophorectomy, or - Medically confirmed post-menopausal status defined as spontaneous cessation of regular menses for at least 12 consecutive months or follicle-stimulating hormone (FSH) and estradiol blood levels in their respective postmenopausal ranges with no alternative pathological or physiological cause.	NA	NA	NA	NA	Although not directly captured in RWD, it is likely to be fulfilled given the alignment with the indication for the exposures of interest	
Inclusion 6	Measurable disease as defined per RECIST v.1.1 (see Appendix 7) or bone-only disease (with bone lesions confirmed by CT, MRI or bone X-ray). Tumor lesions previously irradiated or subjected to other locoregional therapy will only be deemed measurable if disease progression at the treated site after completion of therapy is clearly documented.	NA	NA	NA	NA	It is reasonable to assume that all patients in RWD had measurable disease if they received treatment	
Inclusion 7	World Health Organization Performance Status of 0 to 1	[-90; 0]	ECOG = 0 1	ECOG = 0 1	ECOG = 0 1		edbx_get_ecog()
Inclusion 7	Restriction to period 2015-2022	[0; 0]	Years 2015-2022	Years 2015-2022	Years 2015-2022		

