Exclusion 1	HER2-positive breast cancer	$[-\infty; 0]$	Any HER2+ status prior to or on index date	Any HER2+ status prior to or on index date	Any HER2+ status prior to or on index date	If HER2 is missing and a patient received the exposures of interest, then HER2 is likely to be negative given the alignment with the indication for the exposures of interest	edbx_get_her2()
Exclusion 2	Patients with advanced, symptomatic, visceral spread, that are at risk of life-threatening complications in the short term (including patients with massive uncontrolled effusions [pleural, pericardial, peritoneal], pulmonary lymphangitis, and over 50% liver involvement).	NA	NA	NA	NA	This is a safety criterion for the trial and less relevant to real-world treatment setting, given that patients received treatments of interest	
Exclusion 3	Known active uncontrolled or symptomatic CNS metastases, carcinomatous meningitis, or leptomeningeal disease as indicated by clinical symptoms, cerebral edema, and/or progressive growth. Patients with a history of CNS metastases or cord compression are eligible if they have been definitively treated with local therapy (eg, radiotherapy, stereotactic surgery) and are clinically stable off anticonvulsants and steroids for at least 4 weeks before randomization.	$[-\infty; 0]$	Record of CNS metastases prior to or on index date	Record of CNS metastases prior to or on index date	Record of CNS metastases prior to or on index date		edbx_get_diagnosis_solid()
Exclusion 4	Prior neoadjuvant or adjuvant treatment with a non-steroidal aromatase inhibitor (ie, anastrozole or letrozole) with disease recurrence while on or within 12 months of completing treatment.	[MBC-365; MBC-1]	Treatment with letrozole or anastrozole ≤ 12 months from MBC	Treatment with letrozole or anastrozole ≤ 12 months from MBC	Treatment with letrozole or anastrozole ≤ 12 months from MBC		
Exclusion 5	Prior treatment with any CDK4/6 inhibitor.	$[-\infty; -1]$	Prior treatment with ribociclib, palbociclib, abemaciclib	Prior treatment with ribociclib, palbociclib, abemaciclib	Prior treatment with ribociclib, palbociclib, abemaciclib		
Exclusion 6	Major surgery, chemotherapy, radiotherapy, any investigational agents, or other anti-cancer therapy within 2 weeks before randomization. Patients who received prior radiotherapy to 25% of bone marrow are not eligible independent of when it was received (see Appendix 4).	NA	NA	NA	NA		Proxied by 1st line therapy inclusion

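### First-line status cannot stand in for the surgery and radiotherapy parts of Exclusion 6, and nothing else in the plan restricts, adjusts for or checks them

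*Combined protocol and SAP*

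**What the plan says.** The trial rule behind Exclusion 6 covers "Major surgery, chemotherapy, radiotherapy, any investigational agents, or other anti-cancer therapy within 2 weeks before randomization". It also bars women with extensive earlier marrow irradiation, whenever that was given. Excel appendix Table 1 rates the criterion Relevant and its emulation Limited in all three databases. In Excel appendix Table 2 the time window and all three database cells are NA, and the only implementation is the note "Proxied by 1st line therapy inclusion".

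Section 6.6.4 defines first-line status in EDB1 and EDB3 from a vendor line-of-therapy table, by string match on generic drug names. It states that "The LOT implicitly only considers regimens that were given as part of a metastatic disease setting". For EDB3, "each patient is represented with one row per curated line of therapy AND drug name". For EDB4, used only in sensitivity analysis #11, Excel appendix Table 2 notes that "EDB4 does not have a well-curated line of therapy variable". Section 6.6.4 instead takes the first listed antineoplastic drug on or after the metastasis date.

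Radiation and surgery dates appear once, in Table 4 of section 6.6.5, which the EDB3 outcome text cites. The row beginning "Therapy (cellular, systemic, radiation, surgery" is used there to find the last activity date for censoring.

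**The concern.** A proxy has to carry information about what it replaces. Being on a first line of drug treatment for metastatic disease says nothing about whether a woman was operated on or irradiated in the preceding two weeks. If nothing else in the plan picks this up, women whom the trial would have excluded remain in the cohort, and the factor goes into matching unmeasured.

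Recent radiotherapy or surgery could plausibly mark disease severity and could influence which regimen is started. That is a clinical supposition, not something the documents state. If it is true and the arms differ, the OS hazard ratio is confounded. The balance figures would not show this directly, because the variable is never derived. The study aims at concordance with a trial OS hazard ratio of 0.96, so modest distortions count.

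**Working it through.** **Step 1. What each rule can detect.**

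| Rule (Excel appendix Table 2 unless stated) | Window | Covers |
|---|---|---|
| First-line status (section 6.6.4) | vendor rule | metastatic-setting drug regimens |
| Inclusion 4: "No systemic anti-cancer therapy following initial record potentially indicating metastatic disease and prior to index date" | [MBC; -1] | systemic therapy |
| Exclusion 4 | [MBC-365; MBC-1] | letrozole, anastrozole |
| Exclusion 5 | [-inf; -1] | CDK4/6 inhibitors |
| Exclusion 8 | [0; 0] | systemic therapy |
| Exclusion 6 | NA | nothing directly |

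No row covers surgery or radiotherapy, including the marrow-irradiation rule. Table 5 has no covariate for either, the sensitivity-analysis Table 8 does not vary either, and section 7 does not mention them.

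**Step 2. The chemotherapy part.** Systemic therapy from the metastatic date to the day before index is caught by Inclusion 4, and index-day therapy by Exclusion 8. To escape, chemotherapy must precede the metastatic date and still fall within 14 days of index, so those two dates must themselves lie within about two weeks of each other. This gap is narrow.

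**Step 3. The plan's own precision.** The only stated calculation is the power in section 10.3. With Schoenfeld's formula, two-sided alpha 0.05 and 50% exposed, power = Φ(|ln 0.92| × √(d/4) − 1.96).

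- EDB1, d = 1021: Φ(0.0834 × 15.98 − 1.96) = 0.265 (stated 0.27).
- EDB3, d = 331: Φ(0.0834 × 9.10 − 1.96) = 0.115 (stated 0.11).

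Both reproduce. Pooled events are 1021 + 331 = 1352, so the standard error of the log hazard ratio is about 2/√1352 = 0.054.

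**Step 4. Illustration on assumed inputs.** The documents give no frequency of recent surgery or radiotherapy, overall or by arm. For a binary factor with mortality hazard ratio g and prevalence pC (combination) and pL (letrozole alone), the OS hazard ratio is multiplied by approximately (1 + pC(g − 1)) / (1 + pL(g − 1)).

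| pC | pL | g = 1.3 | g = 1.5 | g = 2.0 |
|---|---|---|---|---|
| 5% | 10% | 0.985 | 0.976 | 0.955 |
| 10% | 20% | 0.972 | 0.955 | 0.917 |
| 10% | 5% | 1.015 | 1.024 | 1.048 |
| 20% | 10% | 1.029 | 1.048 | 1.091 |
| equal | equal | 1.00 | 1.00 | 1.00 |

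A factor of 0.955 is |ln 0.955|/0.054 = 0.046/0.054, or about 0.85 pooled standard errors. The table makes no allowance for partial balancing through correlated covariates. Its prevalences suit a window of weeks to months better than a strict 14 days.

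**Step 5. Reach of a remedy.** Dates are documented for EDB3 only: 331/1352 = 24% of primary matched events. For EDB1, section 6.6.5 mentions only visits and treatment encounters as censoring dates, so availability is unknown for the other 76%.

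**The case against.** A reader might infer that recently irradiated or operated women are unbalanced between the arms and that the hazard ratio is pushed below 1. The documents support neither step. They give no frequency by arm, the balance figures are not visible, and nothing says which arm has more radiotherapy. The propensity score includes number of metastatic sites, time from metastatic diagnosis, de novo status, ECOG and laboratory values, which may balance the factor in part. Exclusion 3 removes women with any recorded CNS metastasis, which may take out some who had palliative radiotherapy. This stands and limits the claim to factors not directly adjusted for or checked. It does not close the gap: Excel appendix Table 1 expects high ECOG missingness, and section 6.7.1 keeps women with missing values eligible, so a near correlate would often be imputed.

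A reader might also infer a concealed omission. It is not one, because the plan itself rates the emulation Limited. What is wrong is the statement that first-line status serves as the proxy.

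Feasibility is a fair objection. Excel appendix Table 1 says most databases give only month- or year-level dates, and Table 5 warns of negative intervals, so a strict [-14;-1] rule may not be workable. Table 4 also lists items from other tumour types, so it may be a general template and does not prove complete capture. Finally, radiotherapy 15 to 90 days before index was not barred by the trial's washout, so a 90-day flag is a severity covariate and does not emulate Exclusion 6.

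**Conclusion.** The point holds in a limited form. First-line status cannot detect recent surgery or radiotherapy, and no other criterion, covariate or sensitivity analysis does, so these parts of a criterion rated Relevant are not directly restricted, adjusted for or checked. The chemotherapy part is largely covered.

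The direction and size of any bias cannot be determined from the documents. The range of about 0.92 to 1.09 rests wholly on assumed prevalences, an assumed mortality hazard ratio and no help from correlated covariates; with equal prevalence there is no bias from this source. This is a worthwhile, inexpensive improvement to the plan, not a demonstrated error in its estimate.

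**What to change.** 1. In both Excel appendix tables, state that the first-line proxy does not cover surgery, radiotherapy or the marrow-irradiation rule. Rate that part as not emulated where dates are unavailable.
2. In EDB3, and in EDB1 only if such dates were delivered, derive a flag for radiotherapy or surgery in [-90;0], the window already used for ECOG and laboratory values. Report it by arm before and after matching.
3. Add the flag to that database's propensity score, labelled as a severity covariate. This follows the commitment in section 6.6.7 that "the most comprehensive model will be fit for each database individually".
4. Exclude women with a recent record only as a sensitivity analysis, with a window that the date granularity supports.

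The cost is one derived variable and a rerun of matching. A changed propensity model may lose a few pairs under the caliper of 1% of the propensity-score standard deviation. Capture of radiotherapy and surgery may be incomplete, so absence of a record should not be read as absence of treatment.
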